#### 9.4.2 Solicited Events and Symptoms

Systemic and local solicited adverse events were collected 60 minutes post-vaccination and then daily for 7 days after vaccination and graded on a scale of 0 (absent), 1 (mild), 2 (moderate) and 3 (severe). Systemic events include: elevated oral temperature, headache, fatigue/malaise, joint pain/arthralgia,

muscle pain/myalgia, diarrhea, anorexia, chills and vomiting. Local events include: pain at injection site, erythema at injection site, and swelling at injection site.

The proportion of participants, within each treatment arm, reporting at least one solicited adverse event will be summarized for each solicited adverse event, any systemic symptom, any local symptom, and any symptoms. The 95% CI calculated using Clopper-Pearson methodology from a binomial distribution (SAS PROC FREQ with a binomial option) will be presented (Table 14.3.1.2).

For each systemic and local event, any systemic event, any local event, and any solicited event, the maximum severity over 7 days after each vaccination will be summarized for the FA population. The number and percentage of participants reporting each event will be summarized by the maximum severity for each treatment group. For each event the denominator is the number of participants with non-missing data for the specific event (Table 14.3.1.3).

The number and percentage of participants reporting any solicited adverse event, any local symptom, any systemic symptom and for each individual symptom will be summarized for each day post vaccination by Treatment group (Table 14.3.1.4). The percent of participants reporting any systemic solicited event and any local solicited event will be displayed graphically in a bar chart in Figures 14.3.1.5.1 and 14.3.1.5.2, respectively.

Fisher's exact test will be used to compare the proportion of participants with solicited local and systemic reactogenicity events between each of the MCV-5 groups and the Menactra® group. The results will be summarized in Table 14.3.1.6.

The primary purpose of the statistical comparisons is to screen out potential solicited reactogenicity events that need further clinical evaluation. Therefore, they are not considered formal statistical hypothesis tests and it is acknowledged that there will be inflated Type I errors (i.e., inflated false statistical significances) from performing multiple unadjusted comparisons.

Solicited adverse events by participant will be presented in Listing 16.2.7.1.1 for systemic events and Listing 16.2.7.1.2 for local events.

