#### **Analysis of Primary Safety Objective**

The primary aim of the study is to assess the safety of the study vaccine. All safety data (solicited local and systemic reactions and unsolicited AEs and SAEs) collected after participants are exposed to the study product will be included in the primary analysis of safety.

To assess safety, the number and percentage of participants experiencing at least one AE, and the number and percentage of participants experiencing each specific AE, categorized by body system and preferred term, will be tabulated by product received along with their corresponding two-sided exact 95% confidence intervals.

Fisher's exact test will be used to compare the proportion of participants with solicited local and systemic reactogenicity events between the MCV-5 group and the Menactra® Group. The primary purpose of statistical comparisons is to screen out potential solicited reactogenicity events that need further clinical evaluation. Therefore, they are not considered formal statistical hypothesis tests and it is acknowledged that there will be inflated Type I errors (i.e. inflated false statistical significances) from performing multiple unadjusted comparisons.

Changes in clinical laboratory values from baseline to end of treatment/follow-up will be analyzed descriptively.

To facilitate the planning of the follow-up trial, analysis of unblinded primary safety data up to Visit 4 (Day 29) by treatment groups will be made available to the Sponsor after all participants have completed this visit and their data have been cleaned and verified.

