#### 4 INVESTIGATIONAL PLAN

#### 4.1 Overall Study Design and Plan

This study is a Phase 1, single center, double blinded, randomized, controlled clinical trial to assess the safety and immunogenicity of the adjuvanted and non-adjuvanted formulation of polyvalent conjugate vaccine composed of serogroups A, C, Y, W and X *Neisseria meningitidis* capsular polysaccharides (MCV-5) as compared to the quadrivalent (ACYW) Menactra® vaccine. As this is the first clinical study with the study vaccine, the study will initially be performed in 60 adult healthy participants aged 18 to 45 years old.

The study will have 3 arms with 3 vaccines given in a 1:1:1 ratio; adjuvanted MCV-5, non-adjuvanted MCV-5 and Menactra®. Each participant will receive a single intramuscular (IM) injection of one of the three vaccines and will be followed up to six months after the vaccination. There will be 20 participants per vaccine group.

The vaccinator will be aware of group allocation, although he/she will not be able to influence or decide this allocation nor be part of the safety assessment. This will ensure that the study team, involved in assessment of safety outcomes, as well as participants, are unaware of the identity of the study vaccine

administered to them. This will help rule out bias at the time of assessment. As the reference product and study vaccines are different in appearance and composition, the vaccinator blind cannot be maintained in this study. However, the vaccinator will not be involved in the safety assessment.

In addition, immunogenicity assessments are planned to evaluate any differences in the immune responses induced by the adjuvanted and non-adjuvanted study vaccines and to compare against the reference vaccine. The study, however, is not statistically powered to determine significance of any difference. A formal sample size calculation was not performed as this is a Phase 1 trial and the first clinical study in humans with the study vaccine.

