#### 8 IMMUNOGENICITY EVALUATION

The secondary and exploratory immunogenicity outcomes for the study are based on the rSBA titer for Meningococcal serogroup A, C, Y, W and X specific antibodies. For each participant, the rSBA titer will be measured at Day 1 prior to vaccination and at Day 29 (28 days post vaccination). All immunogenicity analyses will be conducted using the PP population and FA population. Individual participant data listings of immunogenicity will be presented in Listing 16.2.6.

Due to the hypothesis generating nature of multiple statistical comparisons for immunogenicity associated with multiple endpoints for this early phase FIH study, all estimations will be carried out using a two-sided 5% Type I error rate without an adjustment for multiple comparisons.

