#### 8.1 Secondary Endpoint - a 4-fold response in rSBA titer

The percentage of participants with a 4-fold response in rSBA titer against serogroups A, C, W, Y and X will be defined as follows:

- For participants with a pre-vaccination rSBA < 8, a post-vaccination titer >= 32.
- For participants with a pre-vaccination rSBA titer ≥ 8, a post-vaccination rSBA titer of at least 4 times the pre-vaccination titer.

The number and percentage of participants with a 4-fold response in rSBA titer will be summarized at Day 29, along with two-sided 95% exact confidence intervals (CIs) for each of the proportions. Two-sided exact 95% CIs for the three pair-wise proportion differences between the three treatment groups will be computed using the unconditional exact method proposed by Chan and Zhang (1999).(Note: In SAS, this is the RISKDIFF(METHOD=FMSCORE) option in PROC FREQ).

Table 14.2.1.1 will summarize the number and percentage of participants with a 4-fold response in rSBA titer for each of the five serogroups and 95% CIs for each treatment group and treatment group comparison. CIs will be visualized graphically in Forest plots as depicted in Figure 14.2.1.2.

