N = number of participants in the Full Analysis population.

<sup>1 Fisher's exact 2-tailed test of the proportion of participants with an event.

TABLE 14.3.1.3: Number and Percentage of Participants Experiencing Solicited Events by Symptom, Maximum Severity and Treatment Group - Safety Population

		MO	vanted CV-5 =X)	MO	juvanted CV-5 =X)	Menactra® (N=X)	
Symptom	Severity	n	%	n	%	n	%
Any Symptom	None						
	Mild						
	Moderate						
	Severe						
	Life-Threatening						
Any Local Symptom	None						
	Mild						
	Moderate						
	Severe						
	Life-Threatening						
Pain at Injection Site	None						
	Mild						
	Moderate						
	Severe						
	Life-Threatening						
Erythema at Injection Site	None						
	Mild						
	Moderate						
	Severe						
Swelling at injection site	None						
	Mild						
	Moderate						
	Severe						
	Life-Threatening						

N = Number of participants in the Full Analysis population; Severity is based off of the maximum severity reported post vaccination.

TABLE 14.3.1.3: Number and Percentage of Participants Experiencing Solicited Events by Symptom, Maximum Severity and Treatment Group - Safety Population

		M	vanted CV-5 (=X)	MO	juvanted CV-5 (=X)		actra® =X)
Symptom	Severity	n	%	n	%	n	%
Any Systemic Symptom	None						
	Mild						
	Moderate						
	Severe						
	Life-Threatening						
Elevated Oral Temperature	None						
	Mild						
	Moderate						
	Severe						
	Life-Threatening						
Headache	None						
	Mild						
	Moderate						
	Severe						
	Life-Threatening						
Fatigue/malaise	None						
	Mild						
	Moderate						
	Severe						
	Life-Threatening						
Joint pain/arthralgia	None						
	Mild						
	Moderate						
	Severe						
	Life-Threatening						
Muscle pain/myalgia	None						
	Mild						
	Moderate						
	Severe						
	Life-Threatening						
Diarrhea	None						
	Mild						
	Moderate						
	Severe						
	Life-Threatening						
Anorexia	None						
	Mild						
	Moderate						

TABLE 14.3.1.3: Number and Percentage of Participants Experiencing Solicited Events by Symptom, Maximum Severity and Treatment Group - Safety Population

		MO	vanted CV-5 =X)	MC	juvanted CV-5 =X)	Menactra® (N=X)	
Symptom	Severity	n	%	n	%	n	%
	Severe						
	Life-Threatening						
Chills	None						
	Mild						
	Moderate						
	Severe						
	Life-Threatening						
Vomiting	None						
	Mild						
	Moderate						
	Severe						
	Life-Threatening						

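### Solicited reactions are compared with Menactra by Fisher p-values alone; a risk difference with the unconditional exact interval already planned for immunogenicity would be a more sensitive and informative screen

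*SAP*

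**What the plan says.** Solicited local and systemic reactions are part of the primary endpoint (SAP 3.2.1). On allocation and size, SAP 4.1 says "The study will have 3 arms with 3 vaccines given in a 1:1:1 ratio" and "There will be 20 participants per vaccine group". The method is in SAP 9.4.2: "Fisher's exact test will be used to compare the proportion of participants with solicited local and systemic reactogenicity events". Adjuvanted and non-adjuvanted MCV-5 are each set against Menactra in turn. The footnote to the Table 14.3.1.2 shell describes it as Fisher's "exact 2-tailed test of the proportion of participants with an event". The shell shows n (%) with a 95% interval for each arm (Clopper-Pearson, per SAP 9.4.2) and two p-value columns. It has no column for a difference between arms.

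Protocol 7.5.2 names the same test and gives its role: "The primary purpose of statistical comparisons is to screen out potential solicited reactogenicity events that need further clinical evaluation". Both documents say that these are not formal hypothesis tests and accept inflated Type I error from unadjusted comparisons. Neither states the p-value at which a reaction is flagged. The only level given is for immunogenicity (SAP 8): "all estimations will be carried out using a two-sided 5% Type I error rate without an adjustment for multiple comparisons".

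For the immunogenicity proportions, SAP 8.1 says that exact 95% intervals for the "three pair-wise proportion differences between the three treatment groups will be computed using the unconditional exact method" of Chan and Zhang, and SAP 8.2 repeats this for the titre thresholds.

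**The concern.** In a safety screen a missed excess usually costs more than a false flag, and the plan leans that way by accepting inflated Type I error. Fisher's test pulls in the other direction: with small equal arms its true size is well below the nominal level, so borderline excesses go unflagged.

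The plan is also uneven. A secondary endpoint gets a between-arm estimate with an exact interval. A primary endpoint gets a between-arm p-value only, although Protocol 2.4.1 says that the three-group design will allow the MCV-5 safety profiles to be compared with that of the licensed vaccine. A p-value at 20 per arm tells the reader little about how large an excess remains compatible with the data.

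**Working it through.** **The plan's own figures.** Protocol 7.4 and SAP 5 give a greater than 90% chance of seeing an 11% event in 20 recipients, and a one-sided 95% upper bound of about 14% when none is seen. Both reproduce: 1 − 0.89^20 = 0.903, and 1 − 0.05^(1/20) = 0.139. They concern one arm at a time. The documents give no size or power for the between-arm test.

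**Inputs.** 20 per arm (SAP 4.1); two-sided test (Table 14.3.1.2 footnote); Menactra rates from Protocol 13.2: pain 53.9%, induration 17.1%, redness 14.4%, swelling 12.6%, headache 41.4%, fatigue 34.7%, malaise 23.6%, arthralgia 19.8%, diarrhea 16.0%, anorexia 11.8%, chills 9.7%, vomiting 2.3%. Two inputs are assumptions: a flag at p ≤ 0.05, and an illustrative excess of 30 percentage points.

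**Method.** Enumerate all 21 × 21 outcome tables. With R(a,b) = 1 when the test flags a events on MCV-5 and b on Menactra:

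- size(p) = Σ R(a,b) · Bin(a; 20, p) · Bin(b; 20, p), maximised over p;
- power = Σ R(a,b) · Bin(a; 20, p + 0.30) · Bin(b; 20, p).

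The unconditional p-values are maximised over the common rate. For the score test, two one-sided tests at 2.5% (the Chan-Zhang form) and one two-sided test at 5% give the same flagged tables.

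**Maximum size, 20 vs 20.** Fisher 2.53%, Boschloo 4.64%, unconditional score 4.98%. At the Protocol 13.2 rates, Fisher's size is 2.5% for fatigue, 2.1% for pain, 1.1% for chills and 0.01% for vomiting.

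**Which tables differ.** At 20 vs 20 both unconditional tests flag every table that Fisher flags. In the direction of excess on MCV-5, both also flag ten more: 6 v 1, 8 v 2, 9 v 3, 12 v 5, 13 v 6, 14 v 7, 15 v 8, 17 v 11, 18 v 12 and 19 v 14 (Fisher p 0.054 to 0.092). The score test adds 4 v 0 and 20 v 16 (Fisher p 0.106).

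One example is 8/20 vs 2/20, a difference of 40% − 10% = 30 points. Fisher's two-sided p is 2 × [C(20,8)·C(20,2) + C(20,9)·C(20,1) + C(20,10)] / C(40,10) = 2 × 27,478,256 / 847,660,528 = 0.065. The unconditional score p is 0.039, so the matching 95% interval excludes zero.

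**Power for a 30-point excess, 20 vs 20.**

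| Reaction | Menactra rate | Fisher | Boschloo | Score |
|---|---|---|---|---|
| Pain | 53.9% | 44% | 53% | 53% |
| Headache | 41.4% | 35% | 45% | 45% |
| Fatigue | 34.7% | 34% | 44% | 44% |
| Swelling | 12.6% | 46% | 57% | 57% |
| Chills | 9.7% | 50% | 61% | 62% |
| Vomiting | 2.3% | 67% | 74% | 80% |

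Over all 12 rates the gain is about 6 to 12 points with Boschloo and 8 to 13 with the score test. For 11 of the 12 rates, power after the change is still only about 44% to 62%.

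**Sensitivity to arm size.** Fisher's maximum size is 3.6% at 20 vs 19, 3.5% at 20 vs 18, 2.8% at 19 vs 19 and 2.9% at 18 vs 18. At 20 vs 19 Boschloo's size is 4.2% and its power gain shrinks to about 0 to 4 points (pain 50% to 52%, headache 40% to 44%, chills 52% to 52%).

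**Sensitivity to the flag.** At p ≤ 0.10, Fisher's maximum size at 20 vs 20 is 5.3%.

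**False flags.** The trial solicits 3 local and 9 systemic reactions, so there are 12 × 2 = 24 comparisons. If these were independent and each at its maximum size, the chance of at least one false flag would be 1 − (1 − 0.0253)^24 = 46% with Fisher, and 1 − 0.95^24 = 71% at a full 5% each.

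**The case against.** A reader might infer that Fisher's test is a mistake, or that the trial would overlook safety signals because of it. The documents do not support either reading.

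- Fisher's test is valid, conventional and named in the protocol as well as the SAP.
- Without a stated cut-off, the p-value is not a hard pass/fail rule. Results with Fisher p between 0.054 and 0.106 would still be printed beside both arms' rates and intervals.
- No safety decision depends on these p-values. The safety hypothesis rests on vaccine-related SAEs and tolerability (Protocol 7.1), the pause rules act on one or two events (SAP 6.6.2), and the Safety Review Committee looks at the data weekly (SAP 6.6.1).
- SAP 2.1 says plainly that the study is not powered to show differences.
- The gain is largest at exactly 20 vs 20 and is erratic around it, and SAP 4.3 plans only approximately 60 participants.
- The rates in Protocol 13.2 do not map one-to-one onto the solicited events. They split induration from swelling and fatigue from malaise, which the trial combines, and they give none for fever or myalgia.

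All of this stands, and it limits the point to lost efficiency and a missing estimate. It does not explain why a primary endpoint has no between-arm difference or interval when the method is already planned for the secondary ones. The committee review and the pause rules are not between-arm comparisons and do not fill that gap.

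**Conclusion.** The point holds as an inexpensive improvement, not as an error in the plan. The firm part does not depend on a cut-off or on arm sizes: Table 14.3.1.2 offers no risk difference and no interval for it.

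The efficiency part is conditional. It rests on an assumed two-sided 0.05 flag and on exactly 20 vs 20. There, Fisher works at a maximum size of about 2.5% where unconditional exact tests reach 4.6% to 5.0%, and it gives up roughly 6 to 13 points of power for a 30-point excess. One missing participant in one arm can remove most of Boschloo's gain. No exact test makes this a sensitive screen at 20 per arm, which is a further reason to show the interval rather than lean on a p-value.

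**What to change.** 1. In SAP 9.4.2 and Table 14.3.1.2, add for each solicited event the risk difference (each MCV-5 arm minus Menactra) with a two-sided 95% Chan-Zhang unconditional exact interval, and make this the screening display.
2. If a p-value is kept, either replace Fisher with an unconditional exact test or keep Fisher as supplementary. State the flag level in either case.
3. Make the matching change in Protocol 7.5.2, or record it as a SAP departure. Protocol 7.5.2 refers to a single MCV-5 group where the SAP compares each MCV-5 arm, so align that wording too.
4. Correct the cross-reference in SAP 9.4.2, which sends the Fisher results to Table 14.3.1.6. That shell is for unsolicited events; the p-value columns are in Table 14.3.1.2.

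The cost is a text change in two documents, two more columns, and reuse of code already planned for SAP 8.1 and 8.2. No data collection or design change is needed. The downside is somewhat more false flags, with each test still at or below 5%, in a screen whose Type I error inflation SAP 6.8 already accepts.

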#### 9.4.3 Unsolicited Adverse Events

The proportion of participants reporting at least one unsolicited adverse event will be summarized by MedDRA® system organ class and preferred term for each treatment group and overall. Denominators for percentages are the number of participants in the FA population. A 95% CI calculated using Clopper-Pearson methodology from a binomial distribution (SAS PROC FREQ with a binomial option) will be presented for each MedDRA® system organ class and preferred term (Table 14.3.1.7)

Unsolicited adverse events by participant will be presented in Listing 16.2.7.2.

The following summaries for unsolicited adverse events will be presented by treatment group:

- Participant level summary of maximum severity and relationship to study product by MedDRA® SOC and PT (Table 14.3.1.8.1);
- Participant level summary of related unsolicited events by maximum severity, MedDRA® SOC and PT (Table 14.3.1.8.2);

- Participant incidence of unsolicited adverse events over time by MedDRA® SOC and PT (Days 1-8, Days > 8) (Table 14.3.1.9.1);
- Participant incidence of related unsolicited adverse events over time by MedDRA® SOC and PT (Days 1-8, Days > 8) (Table 14.3.1.9.2);
- Total frequency of adverse events over time by MedDRA® SOC and PT (Days 1-8, Days > 8) (Table 14.3.1.10);
- Participant listing of non-serious adverse events of moderate or greater severity (Table 14.3.2.2);
- Bar chart of the frequency of events for non-serious adverse events by maximum severity and MedDRA® SOC (Figure 14.3.1.11);

#### 9.5 Deaths, Serious Adverse Events and other Significant Adverse Events

A listing of deaths and SAEs (Table 14.3.2.1) will be presented including Participant ID, Adverse Event Description, number of days post dose and number of days post dose it became serious, Reason Reported as an SAE, Relationship to Treatment, Alternate Etiology if not Related, Outcome, Duration of Event (days), and whether participant discontinued due to the AE.

#### 9.6 Pregnancies

For any participants in the FA population who became pregnant during the study, every attempt was made to follow these participants to completion of pregnancy to document the outcome, including information regarding any complications with pregnancy and/or delivery. If more than 5 pregnancies are reported, a table summarizing the total pregnancies, number of live births, and number of spontaneous abortions, elective abortions or still births by treatment will be presented. In addition, a listing of all pregnancies and outcomes will be presented (Listing 16.2.11).

#### 9.7 Clinical Laboratory Evaluations

Safety clinical laboratory evaluations will be performed at Screening and at Day 8 at the site's designated laboratory and will include: hemoglobin (HgB), white blood cells (WBC), platelet counts, alanine transaminase (ALT), albumin, total bilirubin, and creatinine. In addition, screening laboratory tests will include serum HCG pregnancy tests, for females of childbearing potential only, and screening for HIV, HCV and HBV.

The distribution of laboratory results by severity, scheduled study day and treatment group will be presented in Table 14.3.4.1 for any laboratory parameter and each individual laboratory parameter. The observed and change from screening measurements will be summarized using descriptive statistics including mean, standard deviation, median, 25th and 75th percentiles, minimum and maximum values by scheduled study day, for each laboratory parameter in Table 14.3.4.2. Graphical presentation of changes in laboratory values will be presented using box plots as depicted in Figure 14.3.4.3 for each laboratory parameter. Unscheduled or repeated follow-up tests for medical or safety reasons will be listed and included in the maximum post-baseline row on the summary tables, but will otherwise be excluded from tabular and graphical summaries.

Participant visits with abnormal laboratory results, Grade 1 severity or higher, will be presented in Table 14.3.4.4.

Listings of all individual clinical laboratory results will be provided by hematology, biochemistry and serology (Listings 16.2.8.1-16.2.8.3, respectively). Results meeting the protocol defined toxicity of Grade 1 or higher will have their grade provided in parentheses after the result.

